#### **Measurements:**

**1- Children's plaque index** will be measured using simplified oral hygiene index (S-OHI). The plaque scores will be recorded according to the (S-OHI) to assess oral hygiene status for children. The oral examination will be performed using a sterilized disposable examination kit, including a mouth mirror and explorer, in a separate classroom with each student seated on a chair under optimum artificial light.

The examiners will perform an oral examination for children in both groups and record their plaque score before the intervention and after 3 months of intervention. Oral examination will be conducted in the morning hours before the school meal. Children will not be informed about the day of examination to prevent **Hawthorne effect**. **Hawthorne Effect:** It is a psychological phenomenon that occurs when individuals modify their behavior or performance in response to the awareness of being observed.

**2-Mothers' oral hygiene knowledge, attitudes, and practices towards their children**, using a questionnaire. Paper questionnaire will be submitted before the intervention and after 3 months of intervention.

3-Demographic information, parents' socioeconomic condition, dietary habits and oral hygiene performance to reduce confounding factors, using a self-administered questionnaire to complete at home and return to the researchers before conducting the study.

(Accounting for the cultural sensitivity self-administered parental questionnaire will be used. Before conducting the study, the validity and practicality of the questionnaire will be tested.) Evaluations of children's oral hygiene status and mothers' knowledge, attitude and practices toward their children will be recorded before the intervention and after 3 months of intervention for the two groups.

#### By the end of implementing oral health education, we will compare:

The children's oral hygiene status and mothers' knowledge, attitude and practice toward their children between the conventional and non-conventional group.

#### Data collector:

Two dentists will perform the oral examinations. Prior to the commencement of the trial, dentists will be trained and calibrated. Inter-examiner reliability will be measured by repeated examinations in a sample of ten children to assess the inter-examiner agreement of plaque score using Cohen's Kappa statistics.

#### Coding

During data collection, the coding procedure will be carried out. Each child will have a specific code.

#### Data analysis

Descriptive statistics will be used to summarize baseline characteristics. Inferential statistics, including t-tests for continuous variables and Chi-squared tests for categorical variables, will be used to compare outcomes between the two groups. A significance level of p < 0.05 will be used for all analyses.

Children's oral hygiene status, mothers' knowledge, attitudes, and practices will be the dependent variables in this study. Conventional and non-conventional oral health education will be the independent variables.

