### **Study sample:**

Mother-child pair.

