#### Sample size:

The calculation of the sample size for this study was conducted using the OpenEpi (openepi.com). The expected sample size will be 788 mother-child pair at a power of 0.80 and an alpha error of 0.05. To increase the statistical power and account for dropout during the follow-up period, the sample size will be raised by 10%, resulting in an additional 78 mother-child pair. Thus, the total sample size of this study will be 866 mother-child pair. These participants will be divided equally into two groups conventional group and non-conventional group. Each group will consist of 433.

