#### Sampling technique:

In this study we will use a multi-stage stratified random sampling technique.

-At the educational offices level: All three educational offices will be included.

-At kindergarten level: Cluster sampling using stratified proportional sampling technique. This study will include ten kindergartens. The number of kindergartens was determined based on a comprehensive assessment, taking into consideration each educational office's weight and the extent of its children enrollment. This method will ensure that the sample size from each office is distributed proportionally by accounting for the public and private strata.

To select kindergartens from each education office, we will use the Simple Random Sampling (SRS) technique. The names of kindergartens will be listed, assigning a number to each KG. A computer random numbers generator will be used to randomly select KGs to be invited to take part in the study.

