#### -At the children level:

Using a computerized random number generator.

Classes will be randomly allocated into the two study groups (conventional and nonconventional) using a a coin toss.

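### Whole classes are randomised, but outcomes are compared with t-tests and chi-squared tests that treat mother-child pairs as independent, so the 0.05 error rate does not hold

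*Protocol*

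**What the plan says.** The section on sampling at the children level fixes the unit of allocation: "Classes will be randomly allocated into the two study groups (conventional and nonconventional) using a a coin toss". The classes come from sampled kindergartens: "Cluster sampling using stratified proportional sampling technique. This study will include ten kindergartens".

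Everything else is counted in pairs. Study sample gives the unit as "Mother-child pair". Sample size states "The expected sample size will be 788 mother-child pair at a power of 0.80 and an alpha error of 0.05", adds 10% for dropout, and continues: "These participants will be divided equally into two groups conventional group and non-conventional group. Each group will consist of 433".

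Data analysis names the between-group comparison: "Inferential statistics, including t-tests for continuous variables and Chi-squared tests for categorical variables, will be used to compare outcomes between the two groups". It adds: "A significance level of p < 0.05 will be used for all analyses".

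The protocol mentions no class or kindergarten effect, mixed model, GEE, cluster-robust variance or class-level summary. The measures listed under Confounding factors are probability sampling, exclusion criteria, public and private strata, standardisation, and measurement of the expected confounders. None of them deals with correlation between children in one class.

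**The concern.** A t-test or chi-squared test on pairs takes its standard error from the variation between pairs, as if each pair had been randomised separately. Here one coin toss places a whole class. Children in a class share a room and a kindergarten, and kindergarten teachers give the programme in school hours. Any outcome component that they share moves the whole class mean and does not average out over the pairs within the class. The tests leave that component out of the standard error.

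The comparison affected is the one that the hypothesis rests on. It covers every dependent variable: the children's oral hygiene score and the mothers' knowledge, attitudes and practices. The error makes a difference between the programmes too easy to declare, including a claim that the non-conventional programme is superior.

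**Working it through.** **Inputs from the protocol.** Allocation by class (At the children level). t-tests and chi-squared tests at p < 0.05 (Data analysis; sidedness is not stated, so two-sided is assumed). 788 pairs, plus 78, at power 0.80 and alpha 0.05 (Sample size).

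**Inputs not in the protocol, therefore assumed.** Children per class m = 15 to 30. ICC = 0.01 to 0.10. The number of classes is not given either. It cannot be derived, because Sampling technique speaks of ten kindergartens while the sampling fraction after the Al-Hofuf private stratum uses 14.

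**Step 1: the plan's own figure.** The total adds up: 788 + 78 = 866 = 2 × 433. The 788 itself cannot be reproduced, because no effect size, standard deviation or proportions are stated. The usual formula for independent observations comes close at an assumed standardised difference of 0.2:

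2 × (1.96 + 0.8416)² / 0.2² = 392.4, so 393 per arm and 786 in total.

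Proportions of 0.5 and 0.6, also assumed, give 388 per arm and 776 in total. No design effect is mentioned.

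**Step 2: real error rate of the planned test.**

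- Design effect: DE = 1 + (m − 1) × ICC
- Real two-sided error: 2 × [1 − Φ(1.96 / √DE)]

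Example with m = 20 and ICC = 0.05: DE = 1 + 19 × 0.05 = 1.95, 1.96 / √1.95 = 1.404, error = 16.0%.

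| Children per class | ICC 0.01 | ICC 0.02 | ICC 0.05 | ICC 0.10 |
|---|---|---|---|---|
| 15 | DE 1.14, 6.6% | DE 1.28, 8.3% | DE 1.70, 13.3% | DE 2.40, 20.6% |
| 20 | DE 1.19, 7.2% | DE 1.38, 9.5% | DE 1.95, 16.0% | DE 2.90, 25.0% |
| 25 | DE 1.24, 7.8% | DE 1.48, 10.7% | DE 2.20, 18.6% | DE 3.40, 28.8% |
| 30 | DE 1.29, 8.4% | DE 1.58, 11.9% | DE 2.45, 21.1% | DE 3.90, 32.1% |

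**Step 3: check by simulation, with no true effect.** With 28 to 58 equal classes and 6,000 trials per setting, the t-test on individuals rejected in 6.4% to 32.3% of trials over the same grid. A t-test on class means rejected in 4.7% to 5.3%. A second simulation used 40 coin-tossed classes of 12 to 28 children and 4,000 trials per setting. The individual test rejected in 7.1%, 10.3%, 16.8% and 27.2% at the four ICC values, and the test on class means in 4.7% to 5.9%.

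**Step 4: what a valid analysis does to power.** The effective number of independent pairs is 788 / DE. It runs from 788 / 1.14 = 691 (m = 15, ICC 0.01) to 788 / 3.90 = 202 (m = 30, ICC 0.10). If 788 rests on a standardised difference of about 0.2, power falls from 0.80 to between about 0.75 and 0.29.

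**The case against.** Data analysis does not name the unit of analysis. A t-test on class means is still a t-test, and the simulations show that it holds its level. The list of methods is also open-ended, and a statistical analysis plan that is not shown could add a cluster method. So the individual-level reading is an inference. It is a strong one: the pair is the only unit in Study sample and Sample size, and a chi-squared test on categorical outcomes is naturally a test on individuals. The protocol does not merely leave a detail open. It names tests that, run on the unit it counts, do not fit its own allocation.

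The size is uncertain, and that stands. At an ICC of 0.01 the error rate is only 6.6% to 8.4%, and at zero there would be no inflation. Children may also be sampled within classes, which makes the analysed clusters smaller.

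The protocol does not say that each class has its own teacher. The weekly game is played online from home, in the non-conventional arm only. Mothers choose between attending in person and online, with no grouping by class. Shared delivery is therefore better documented for the children's score than for the mothers' answers. The argument does not depend on this: allocation by class and some positive correlation are enough.

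Finally, if classes of one kindergarten fall into both arms, part of the kindergarten-level variation can be removed from the comparison. The coin toss does not guarantee that balance, an unadjusted t-test would not use it, and the class-level correlation remains.

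**Conclusion.** The concern holds. The planned tests do not match the unit of randomisation, and with any positive within-class correlation the stated 0.05 level is exceeded for every outcome. The direction is certain under that condition. The size rests on assumed class sizes and ICCs: about 7% to 25% with 20 children per class, and 6.6% to 32% over class sizes of 15 to 30, for ICCs of 0.01 to 0.10. This must be corrected before the analysis, because it affects the trial's main comparison.

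**What to change.** Replace the sentence on inferential tests in Data analysis with text along these lines:

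- The class is the unit of randomisation, and every between-group analysis allows for it.
- The oral hygiene score and the knowledge, attitude and practice scores are compared with a linear mixed model. It has a random intercept for class, a fixed effect for kindergarten or for office by public/private stratum, and Kenward-Roger or Satterthwaite degrees of freedom.
- Categorical outcomes are compared with the matching mixed logistic model, or with GEE clustered on class and a small-sample correction.
- The ICC of each outcome is reported.

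The choice between kindergarten and stratum should be made in advance. A kindergarten with one class, or with all its classes in one arm, adds nothing to a comparison within kindergartens, and some listed kindergartens are very small. The stratum version avoids this. An analysis of class-level summaries would be a simpler valid alternative.

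**Cost.** The analysis text changes, and the class must be stored with each child's code. The class has to be known for allocation, so no new measurements are needed. Confidence intervals become wider. The sample size section should then state the assumed effect, ICC, class size and design effect. With 20 children per class, keeping the precision implied by 788 independent pairs would take 788 × 1.19, or 938 pairs, at an ICC of 0.01 and 788 × 2.90, or 2,286 pairs, at 0.10, before dropout. If recruitment stays at 866, the lower power should be stated openly.

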### **Null Hypothesis**

There is no difference between conventional and non-conventional oral health education on oral hygiene status of preschool children, and on mothers' oral hygiene knowledge, attitude, and practices towards their children.

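### Four equally ranked outcomes are each tested at 0.05 with no primary outcome or success rule, so the stated alpha of 0.05 and power of 0.80 do not apply to the joint hypothesis

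*Protocol*

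**What the plan says.** The Data analysis section lists the outcomes without ranking them: "Children's oral hygiene status, mothers' knowledge, attitudes, and practices will be the dependent variables in this study". T-tests or Chi-squared tests "will be used to compare outcomes between the two groups", and then "A significance level of p < 0.05 will be used for all analyses".

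The same four outcomes appear together in the Aim, the comparative Objective, the Hypothesis and the Null Hypothesis. The null of no difference is stated "on oral hygiene status of preschool children, and on mothers' oral hygiene knowledge, attitude, and practices towards their children". The section on the comparison at the end of the programme again sets them side by side: "The children's oral hygiene status and mothers' knowledge, attitude and practice toward their children between the conventional and non-conventional group".

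The Sample size section says "The expected sample size will be 788 mother-child pair at a power of 0.80 and an alpha error of 0.05". It gives no outcome, effect size, standard deviation or proportions.

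Nowhere does the protocol call an outcome primary, order the tests, adjust for several tests, or say whether one, some or all of the outcomes must be significant for the hypothesis to be supported.

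**The concern.** A trial with one hypothesis over four outcomes needs a rule that links the four test results to a conclusion. This protocol fixes the per-test level but leaves the rule open, and neither natural way of filling the gap delivers what the Sample size section promises.

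- If one significant outcome is enough, the overall error exceeds 0.05.
- If all four are needed, the overall power falls below 0.80.

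The gap matters more because the outcomes are not equally protected from bias. The section on ascertainment and observer bias provides for blinded examiners, which covers the S-OHI score. The other three outcomes come from a questionnaire that the mothers complete themselves, in a trial described as single-blinded. Nothing in the protocol prevents a positive conclusion from resting on those three alone.

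An analysis plan may well settle the order or adjustment of secondary tests. The choice of main outcome, and of the outcome that the sample size is meant to serve, belongs in the protocol. A later plan that adjusted the tests would also depart from the sentence fixing 0.05 throughout.

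**Working it through.** **Inputs from the protocol.** Four dependent variables and 0.05 per test (Data analysis); a null of no difference, read as two-sided (Null Hypothesis); 788 pairs, power 0.80, alpha 0.05 (Sample size).

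**Assumed inputs.** The correlations between outcomes, which the protocol does not give, so a range is shown. For the power calculation, 80% power for each test separately.

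**1. The plan's own figure.** The 788 cannot be reproduced, because no outcome or effect is stated. 394 per arm would fit a standardised difference of about 0.20 (393 per arm) or, for example, 45% against 55% (392 per arm), but the protocol states neither. The dropout step does reproduce: 10% of 788 is 78.8, taken as 78; 788 + 78 = 866; 866 / 2 = 433 per group. The quoted power therefore cannot be traced to any of the four outcomes.

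**2. Any one significant result counts, all nulls true.**

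Independent outcomes: 1 − (1 − 0.05)^4 = 1 − 0.8145 = 18.5%.

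Correlated outcomes, normal test statistics, two-sided at |z| > 1.96:

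| Correlation assumed | Family-wise error |
|---|---|
| All four at 0.3 | 17.4% |
| All four at 0.5 | 15.6% |
| All four at 0.7 | 13.0% |
| All four at 0.9 | 9.4% |
| Maternal scores 0.3 with each other, 0.2 with S-OHI | 17.7% |
| Maternal scores 0.5 with each other, 0.2 with S-OHI | 16.7% |
| Maternal scores 0.7 with each other, 0.2 with S-OHI | 15.2% |

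If the three maternal scores were one combined, independent outcome, there would be two tests: 1 − 0.95^2 = 9.75%.

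Counting only false results in favour of the non-conventional arm, with independence: 1 − 0.975^4 = 9.6%, against 2.5% for a single test. With the last correlation pattern in the table it is about 7.6%.

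**3. All four must be significant, each test with 80% power.**

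Independent outcomes: 0.80^4 = 41%.

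Maternal scores correlated 0.3, 0.5 or 0.7 with each other and 0.2 with S-OHI: about 48%, 51% and 55%.

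On this reading the type I error is not inflated. The loss is in power.

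**The case against.** A reader might infer that the protocol lets superiority be claimed from whichever outcome turns out significant, and that the trial's false-claim rate is therefore 15-19%. The protocol does not say this. It fixes a level for each test, not a decision rule, and the Hypothesis and Null Hypothesis join the outcomes with a conjunction that can equally mean all four are required. On that reading there is no error inflation at all.

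Further points against a single headline figure stand:

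- The correlations are assumptions, and 15% is not a floor.
- The count of four is the natural reading of Data analysis. However, the Measurements section takes knowledge, attitudes and practices from one questionnaire, so a combined score is conceivable, giving 9.75%.
- The two-sided figure counts errors in both directions. Errors favouring the non-conventional arm alone are about half as frequent, although the inflation relative to the 2.5% of a single test is similar.
- The calculation takes each test to hold 5%. Classes are allocated by coin toss while ordinary t-tests and Chi-squared tests are planned, so the true per-test error may be higher. That is a separate matter and is not in these figures.

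These points make the figures conditional. They do not remove the fault, because no reading of the protocol as written gives both a 5% error and 80% power for the joint hypothesis.

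**Conclusion.** The point holds as a conditional one. The protocol ranks four outcomes equally, applies 0.05 to each, and gives neither a primary outcome nor a success rule, while its power and alpha belong to no outcome.

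The size depends on which reading is taken:

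- **Any one suffices:** about 15-19% for independent to moderately correlated outcomes, and lower but still well above 5% under strong common correlation or a single maternal score.
- **All four required:** joint power about 41-55%, given 80% for each test.

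The change should be made, ideally before any outcome is compared between groups, because a primary outcome chosen after the results are seen would carry little weight.

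**What to change.** 1. Name the child's S-OHI score at 3 months as the single primary outcome, tested at two-sided 0.05. It is already planned and is the outcome that the blinded examiners assess.
2. Restate the Sample size section for that outcome: give the assumed difference and variability (or proportions) and the power that the planned number provides.
3. Make mothers' knowledge, attitudes and practices secondary. Test them only if the primary is significant, with Holm at 0.05 across the three.
4. Limit the sentence that sets 0.05 for all analyses to match.

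**Cost.** No further enrolment, visits or data collection. The sample-size statement must be reworked, which takes more than an edit because its assumptions are not recorded. The smallest maternal p-value faces 0.05 / 3 = 0.017. If S-OHI is not significant, the maternal results become exploratory, which is a real concession because they feature in the aim and the comparative objective. Holm does not cure bias from unblinded self-report, which needs separate attention.

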# **Methodological issues:**

Random errors: Eliminating random error completely is unattainable, as the study is restricted

to a sample from the population, not the entire population.

# **Systematic errors**

# Loss of follow-up

This is the main issue because it is a follow-up study.

Minimize by:

**In design level:** Sample size will be raised by 10% to account for any participant loss during the follow-up period.

In conducting level: Maintaining good communication and offer incentives.

# Ascertainment and Observer bias

This can effect the validity of the study and lead to inaccurate conclusions about a intervention efficacy

Minimize by:

In design level: Blinding of examiners, training for examiners, and applying a stringent protocols.

# **Responder bias**

This bias can impact the validity and reliability of study results.

Minimize by:

# In conducting level:

-Ensure participant's anonymity and confidentiality.

-Establish a trusting environment to encourage honest responses from participants.

# **Measurements errors**

This can reduce the precision of study findings.

Minimize by:

# In conducting level:

-Clear explanation to the examiners about the measurement methods that will be used in the study.

-Using disclosing agent help to make individual measurements as precise as possible.

# **Confounding factors**

There are variables that are not the main focus of the study but can potentially affect the study's outcome, leading to erroneous or misleading conclusions. The expected confounding factors for this study include but are not limited to parents' demographic information, socioeconomic condition, dietary habits and oral hygiene performance.

#### Minimize by:

#### In design level:

-Randomization, using probability sampling techniques.

-Restriction, by applying exclusion criteria.

#### In conducting level:

-Stratification, by applying public and private strata.

-Standardization, by applying stringent protocols, and by training and calibration of examiners.

-Check and measure the expected confounding factors.

### **Ethical considerations**

This study will obtain approvals from:

-Internal Research Board (IRB) Approval from internal department of college of dentistry.

-Deanship of Scientific Research Approval from King Faisal University (KFU).

-Formal Approval from Ministry of Education (MOE).

-Formal Approval from each kindergarten (KG) administration.

-Informed consent from each child's guardian.

Participant's confidentiality will be protected. Research data will be preserved by using participant codes in all data and will be stored securely.

